APPENDIX A.1: Planned laboratory tests	64
Appendix B. Definitions for Adverse Events Monitoring	65
APPENDIX C: Clinical adverse events to be monitored : Symptoms	66
APPENDIX D: LABORATORY VALUES	67
APPENDIX E. FEVER SEVERITY GRADING	69

LIST OF ABBREVIATIONS

[figure not shown]
AE	Adverse Event
CFR	Code of Federal Regulations
CIOMS	Council for International Organizations of Medical Sciences
CONSORT	Consolidated Standards of Reporting Trials
CRF	Case Report Form
DSMB	Data and Safety Monitoring Board
DSMP	Data Safety Monitoring Plan
EC	Ethics Committee
FWA	Federal-Wide Assurance
GCP	Good Clinical Practice
IATA	International Air Transit Association
ICH	International Conference on Harmonisation
IND	Investigational New Drug Application
INS	Peruvian National Institute of Health (Instituto Nacional de Salud)
IRB	Institutional Review Board
CITI	Collaborative Institutional Training Initiative
LR or Lr	Lactobacillus reuteri
MOP	Manual of Procedures
NIDDK	National Institute of Diabetes and Digestive and Kidney Diseases
NIH	National Institutes of Health
OHRP	Office for Human Research Protections
OHSR	Office of Human Subjects Research
PI	Principal Investigator
PID	Personal Identifying Code
PL	Placebo
QA	Quality Assurance
QC	Quality Control
SAE	Serious Adverse Event
SID	Specimen identification code
SOP	Standard Operating Procedure
WHO	World Health Organization

PROTOCOL SUMMARY

Title:	Safety of Lactobacillus reuteri in healthy children aged 2-24 months
Précis:	Phase I double blinded randomized trial of the safety and tolerability of Lactobacillus reuteri DSM 17938 given for five successive days in healthy children. Sixty children will receive study product at a treatment to placebo ratio of 2:1 and followed for 3 months for safety outcomes.

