Objectives:	
Primary: To assess the safety and tolerability of Lactobacillus reuteri (Lr) strain DSM 17938 in healthy infants and children. Safety will be assessed through the evaluation of adverse effects in both study arms for 90 days following product administration and by laboratory monitoring of CBC, AST, ALT, T. bilirubin, BUN and creatinine prior to product or placebo administration with follow-up assessment at 5 and 28 days. Tolerability will be assessed based on parental report of subjective symptoms of well-being during product administration and thru D28 of the study.
 
Secondary: To evaluate the duration of shedding of Lactobacillus reuteri (Lr) strain DSM 17938 following administration. This will be determined by and endpoint PCR assay for L. reuteri done on stool collected on D3, D5, D12, D15, D18, D24, D28, D36 on all participants.

Population:	The sample size of sixty is expected to include an equal number of healthy boys and girls 2-24 months of age at the time of enrollment from a rural community in Loreto Peru where chronic undernutrition and diarrheal disease are both highly prevalent.
Phase:	I
Number of Sites:	Single site- Loreto, Peru
Study Duration:	7 months
Subject Participation Duration:	3 months
Description of Agent or Intervention:	
1. Active Product: Description Lactobacillus reuteri 17938 suspended in sunflower oil, medium chain triglyceride oil, silicone dioxide. Total viable count of L. reuteri 17938 1×10^8 CFU/5 drops per day for 5 consecutive days
 
2. Placebo: Composition Sunflower oil, medium chain triglyceride oil and silicon dioxide. Total viable count of L. reuteri is zero CFU/ 5 drops.

Estimated Time to Complete Enrollment:	4 months

Schematic of Study Design:

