4 STUDY DESIGN

The study is a single center Phase 1 double blind placebo controlled trial of *Lactobacillus reuteri* DSM 17938 in children aged 2-24 months. The study population is based in a community with a registered clinical trial center in rural Peru where this protocol can be done in a highly controlled setting. The study is intended to enroll healthy children living in a resource constrained setting where chronic undernutrition and diarrheal disease is common, as this is the population that is most likely to receive benefit from the use of this and or other probiotic products for the treatment of acute infectious diarrhea and environmental enteropathy.

Up to 100 subjects will be enrolled in order to obtain the randomization of 60 subjects, who will receive study product or placebo at a ratio of 2:1. Participants will be enrolled between the ages of 8 weeks and 24 months. There will be no age stratification. Participants will be screened with a baseline history and physical examination and laboratory tests to determine the HIV status of the child, as well baseline laboratory tests to evaluate occult infections, hepatic function, and renal function. Upon randomization subjects will be screened and randomized to a treatment arm. Product will be administered under the direct supervision of study staff daily for 5 days. The primary outcome is the safety and tolerability of the product at this dose and formulation. Safety will be assessed by the monitoring of baseline laboratory tests at 5 and 28 days following the initiation of therapy and by AE monitoring. Tolerability will be evaluated by analyzing 28 day diary cards that are distributed to all randomized subjects on which parents record their child's symptoms (specifically fever, anorexia/oral intake, vomiting, diarrhea, irritability, rash, wheezing, or open fields which allows them to describe any issue their child may experience and grade its severity). Secondary outcomes include: 1) The assessment of the duration of shedding of *Lactobacillus reuteri* (Lr) strain DSM 17938 following administration. This will be determined by and endpoint PCR assay for *L. reuteri* done on stool collected on D3, D5, D12, D15, D18, D24, D28, D36 on all participants.

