9.2 Methods and Timing for Assessing, Recording, and Analyzing Safety Parameters

9.2.1 Adverse Events

Adverse Event: ICH E6 defines an AE as any untoward medical occurrence in a patient or clinical investigation subject administered a pharmaceutical product regardless of its causal relationship to the study treatment. An AE can therefore be any unfavorable and unintended sign (including an abnormal laboratory finding), symptom, or disease temporally associated with the use of study product including active or placebo.

1
2 According to the U.S. DHHS Common Rule an AE **does** include any:

3
4

- exacerbation of a pre-existing illness, such as asthma.
- increase in frequency or intensity of a pre-existing episodic event or condition.
- condition detected or diagnosed after study product administration even though it may have been present prior to the start of the study.
- continuous persistent disease or symptoms present at baseline that worsen following the start of the study.
- symptoms associated with disease not previously reported by the subject will be recorded as an AE.

12
13 According to the U.S. DHHS Common Rule

14 (<http://www.hhs.gov/ohrp/policy/advevntguid.html>) an AE **does not** include a/an:

15

- medical or surgical procedure (eg, surgery, circumcision, transfusion); the condition that leads to the procedure is an AE.
- pre-existing diseases or conditions present or detected at the start of the study that do not worsen.
- situations where an untoward medical occurrence has not occurred (eg, hospitalization for elective surgery, social and/or convenience admissions).

21
22 All AEs including local and systemic reactions not meeting the criteria for “serious
23 adverse events” (See Section 9.2.2) will be captured on the ADVERSE EVENT CRF.
24 Information to be collected includes event description, time of onset, clinician’s (MD)
25 assessment of severity, relationship to study product and time of
26 resolution/stabilization of the event. All AEs occurring while on study product or within
27 90 days of follow-up must be documented appropriately regardless of relationship to the
28 study product. All AEs will be followed to adequate resolution.

29
30 Any medical condition that is present at the time that the subject is screened will be
31 considered as baseline and not reported as an AE. However, if it deteriorates at any
32 time during the study, it will be recorded as an AE.

33

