34 **Specific AEs that will be monitored in this project:**

35
36 During probiotic therapy, study field workers will monitor for other potential adverse effects
37 during their home visits, based on parental interview and information recorded on a study
38 log. **Expected AEs** that are common in this study population will include fever,
39 nausea/upset stomach, vomiting, diarrhea, irritability, rash, pruritis, and wheezing or
40 bronchospasm. Diarrhea episodes will be characterized as watery or dysenteric. Space
41 will also be provided for the open end documentation of any other symptom which could

1 potentially be related to probiotic use. Appendix B and D details expected AEs and how
2 they will be graded by severity. Grading of AEs will be confirmed by the project
3 physician. AEs not listed as Expected AEs in the Toxicity Table will be reported but not
4 graded for severity. Responses to AEs encountered will be at the discretion of the project
5 physician and study monitor, based on type of AE encountered and its severity.

6 **Severity of Event:** Expected AEs will be assessed by the clinician using a protocol
7 defined grading system. For events not included in the protocol defined grading
8 system, the following guidelines will be used to quantify intensity.

9
10 Level 1 = Mild (awareness of a symptom but the symptom is easily tolerated)

11
12 Level 2 = Moderate (discomfort enough to cause interference with usual activity)

13
14 Level 3 = Severe (incapacitating; unable to perform usual activities; requires change in
15 intensity of caregiver activity or bed rest)

16
17 Level 4 = Life threatening

18
19 Changes in the severity of an AE will be documented to allow an assessment of the
20 duration of the event at each level of intensity to be performed. Adverse events
21 characterized as intermittent require documentation of onset and duration of each
22 episode.

23
24 **Method, Frequency, and Time Period for Detecting AEs**

25 At each visit, after the parent of the subject has had an opportunity to spontaneously
26 mention any problems, the investigator will inquire about AEs by asking the following
27 standard questions of the parent:

28 "Has your child had any (other) medical problems since your last visit/assessment?"

29 "Has your child taken any new medicines, other than those given to you in this study,
30 since your last visit/assessment?"

31

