18 will be analyzed, except in the case that the physician or study team deems them to be
19 more severe than reported (the study team may upgrade, but NOT downgrade the
20 severity of the symptom).

21
22 Specific outcome parameters in this category include:

23
24 a. Frequency and severity of symptoms monitored as AEs (adjusted for number of
25 subjects per group)
26 b. Frequency of all AEs (adjusted for number of subjects per group)
27 c. Frequency of SAEs (adjusted for number of subjects per group)

28
29 All continuous variables will be summarized using descriptive statistics including number
30 (N), mean, standard deviation (SD), median, maximum, and minimum. All categorical
31 variables will be summarized using frequency counts and percentages.

32
33 Changes from baseline temperature and fever graded by defined toxicity categories will
34 be summarized using descriptive statistics by treatment group.

35
36 Concomitant medications, including those taken prior to study drug administration, will be
37 listed by subject. All concomitant medications taken after initiation of the study treatment
38 will be tabulated overall and by formulation. The number and percentage of subjects who
39 take at least 1 concomitant medication and the number and percent of subjects who take
40 each specific concomitant medication will be presented.

41
42 Treatment-emergent AEs will be defined as any event with a start date occurring on or
43 after treatment Day 1 or, if pre-existing, worsening after treatment Day 1. If a subject
44 reports the same AE more than once, then that subject will only be counted once for the

1 summary of that AE, using the most severe intensity.

2
3 Treatment-emergent AEs will be summarized as follows to the DSMB during closed
4 sessions:

5 • All treatment-emergent AEs;
6 • All treatment-emergent AEs by intensity;
7 • SAEs;
8 • All treatment-emergent SAEs by relationship to study drug; and
9 • AEs that led to premature discontinuation of study drug.

10 All SAEs and AEs leading to premature withdrawal from the study will be listed.

11
12 Hematology and blood chemistry parameters will be summarized at baseline and at the
13 end of the study. Laboratory values and changes from baseline in laboratory values will
14 be summarized descriptively for all subjects and by treatment group. A summary of shifts
15 from baseline to final evaluation will be given for each parameter for all subjects and by

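### The treatment-emergent AE tables have no onset window: with each child counted once at worst grade, a dosing-period event cannot be told from later background illness

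*Combined protocol and SAP*

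**What the plan says.** The design is in the Protocol Summary: "Sixty children will receive study product at a treatment to placebo ratio of 2:1 and followed for 3 months for safety outcomes". That makes 40 active and 20 placebo. Section 4 fixes the exposure: "Product will be administered under the direct supervision of study staff daily for 5 days".

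The safety objective in the Protocol Summary rests on "evaluation of adverse effects in both study arms for 90 days following product administration". Section 9.2.1 agrees: AEs arising on product or within "90 days of follow-up must be documented appropriately regardless of relationship to the" product.

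Section 11.1 then sets the analysis rule. "Treatment-emergent AEs will be defined as any event with a start date occurring on or" after treatment Day 1, or a pre-existing event that worsens after Day 1. No last onset day is given. If a subject "reports the same AE more than once, then that subject will only be counted once for the" summary of that AE, and the most severe intensity is used. Five summaries for the closed DSMB sessions follow. None is split by onset, and relationship to product is tabulated for SAEs only.

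On background illness, Section 4 places the trial in a "resource constrained setting where chronic undernutrition and diarrheal disease is common". Section 9.2.1 names expected AEs "that are common in this study population will include fever", with vomiting, diarrhea, irritability, rash and others.

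**The concern.** If the product causes a short-lived intolerance, it should show mainly during dosing and soon after. The treatment-emergent AE tables pool that short period with about twelve further weeks in which the same symptoms are expected anyway. Two things follow.

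- **Timing is lost.** An active child with diarrhea on D2 and a placebo child whose only diarrhea is on D70 each add one to the same row.
- **Grade can be overwritten.** A child with mild diarrhea on D3 and severe diarrhea on D70 appears as one severe case.

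The plan recognises that timing matters. Section 9.2.1 makes a temporal relation part of the definition of an associated AE, and Section 7.5 delays iron after the last dose so that its side effects do not confound AE assessment. But for non-serious AEs the planned tables show neither timing nor relationship. The halting rules (Sections 9.5 and 11.3.1) turn on SAEs, so non-serious intolerance can be seen only in these tables and in the diary comparison. Two similar 90-day percentages could be read as support for a well-tolerated product when they mostly reflect background illness.

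**Working it through.** **Nothing to reproduce.** The plan states no AE rate, effect size, alpha or power. Section 11.2 bases the sample size on precedent, and AEs are summarised descriptively. What follows is an illustration on assumed rates.

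**From the documents:** 40 active, 20 placebo; doses on days 1-5; diary cards collected on day 28; AEs documented to day 90.

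**Assumed:** a constant background rate λ of 1 to 8 episodes per child-year for one AE term; the product causes one event in days 1-5 in a share q = 0.20 of active children; complete capture to day 90; and, for power only, a two-sided 0.05 Fisher exact test, which the plan does not propose.

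**Formulas**, for onset up to day w:

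- Placebo children with at least one event: p0(w) = 1 − exp(−λw/365)
- Active children: pa(w) = 1 − (1 − p0)(1 − q)
- Difference in a once-per-child table: pa − p0 = q(1 − p0)
- Share of the product-caused excess still visible: 1 − p0 = exp(−λw/365)

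**Example, λ = 4.** For days 1-5: exp(−4×5/365) = exp(−0.055) = 0.947, so the difference is 0.20 × 0.947 = 18.9 points. To day 90: exp(−4×90/365) = exp(−0.986) = 0.373, so the difference is 0.20 × 0.373 = 7.5 points. Expected active children with a background event: 40 × 0.053 = 2.1 by day 5, and 40 × 0.627 = 25.1 by day 90.

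| λ per child-year | Share visible D1-5 | to D28 | to D90 | Difference D1-5 vs D90 (points) | Fisher power D1-5 vs D90 |
|---|---|---|---|---|---|
| 1 | 99% | 93% | 78% | 19.7 vs 15.6 | 52% vs 18% |
| 2 | 97% | 86% | 61% | 19.5 vs 12.2 | 48% vs 10% |
| 4 | 95% | 74% | 37% | 18.9 vs 7.5 | 41% vs 8% |
| 6 | 92% | 63% | 23% | 18.4 vs 4.6 | 35% vs 5% |
| 8 | 90% | 54% | 14% | 17.9 vs 2.8 | 30% vs 5% |

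**Overwriting of grade.** A child with a dosing-period event has at least one later episode of the same AE in the 85 days from D6 to D90 with probability 1 − exp(−85λ/365). This is 21% at λ = 1, 61% at λ = 4 and 75% at λ = 6. These are ceilings, because only a worse later episode replaces the grade.

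**Capture after day 28.** Section 9.2.2 (post-study AEs) ends active seeking at day 28. After that, Section 7.5 relies on parents reporting febrile illness and on one contact at 3 months. Mild late episodes would be missed more often, so the true share visible lies between the D28 and D90 columns.

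**The case against.** A reader might infer that the whole safety comparison loses its contrast, or that fever is the only symptom analysed over a bounded period. The documents do not support either reading.

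- The Protocol Summary sets tolerability during administration and through D28, Section 4 bases it on 28-day diary cards, and Appendix A collects the cards on D28. An episode on D70 cannot enter that comparison.
- Section 11.1 compares the prevalence of daily symptoms between groups. Its symptom-frequency outcome is adjusted for group size and is not expressly limited to one event per child.
- Fever on days 1-5, temperature, day 5 and day 28 laboratory values, and *L. reuteri* bacteremia fall outside the once-per-child rule. The table of AEs leading to discontinuation of study drug is on-treatment by nature.
- Counting a child once at worst grade is a usual convention. No formal AE test is planned.
- The size of the dilution rests on background rates the documents do not give. At 1 episode per child-year it is modest.
- Details of the DSMB reports sit in a separate Data and Safety Monitoring Plan, not available here, which may already show AEs by onset.

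All of this stands, and it confines the point to the treatment-emergent AE tables. It does not remove it. Section 11.1 gives those tables no last onset day and no onset split, and it gives the diary comparison no method and no separate dosing period.

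**Conclusion.** The point holds for the treatment-emergent AE tables in Section 11.1 and no further. The fault is the missing onset period, not the once-per-child convention. For AEs that are common in this population, the tables cannot separate dosing-period events from later background illness, and a worse later episode sets the grade. For rare events the effect is negligible.

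The size is conditional. If background rates are 1, 4 or 6 episodes per child-year and capture is complete, 78%, 37% or 23% of a product-caused excess stays visible at day 90, against 99%, 95% or 92% within days 1-5. Under-capture after day 28 would lessen the loss, but it would also make the 90-day total a mixture of unequal ascertainment, which is a further reason to split at D28.

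This is a cheap improvement in how the AE tables can be read, not a flaw that undermines the trial. Splitting by onset does not make the trial well powered: for a 20-point excess, power within days 1-5 is still only about 30% to 52% on these assumptions.

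**What to change.** In Section 11.1, tabulate treatment-emergent AEs by arm and onset period:

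1. a prespecified dosing or short post-dose period, for example D1-5 or D1-8 (the documents dictate neither, so choose one before unmasking);
2. from there to D28, the end of active surveillance and of the diary;
3. D29-90.

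Apply the once-per-child, worst-intensity rule within each period. Read tolerability mainly from the periods up to D28, and keep the 90-day total as a supporting table. State beside the D29-90 table that AEs were not actively sought after D28, and reconcile Section 9.2.1 (90 days) with Section 9.2.2 (day 28) on this. Section 7.5 also mentions six weeks of parental recording and a day-36 end, so confirm D28 as the cut.

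Cost: wording in one section and a few more tables. Section 9.2.1 already requires time of onset, and the onset and duration of each intermittent episode, so no new data are needed. The downside is small counts per period with 40 and 20 children. These should be read as description.
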